4.1.1 Part 1 (Dose Escalation)

The first part of the study is dose escalation, where cohorts of patients will receive ascending oral doses of HMPL-306 to determine MTD and/or the recommended phase 2 dose (RP2D). The modified toxicity probability interval-2 (mTPI-2) ([Greenberg 2012](#), [Guo 2017](#)) design will be used to perform dose escalation and MTD/RP2D determination. Briefly, the mTPI-2 method uses a Bayesian framework and a hierarchical model to compute the dose escalation based on the interval between the toxicity rate of each dose level and target probability ([Greenberg 2012](#), [Guo 2017](#)). This study is designed targeting a dose-limiting toxicity (DLT) rate of 20% with an equivalence interval of 15% to 25%.

Like the 3+3 design, the mTPI-2 method incorporates prespecified escalation rules that can be presented in a table ([Table 5](#)). As shown in [Table 5](#), the number of patients dosed at a given dose level are shown in the columns, while the rows indicate the number of DLTs experienced. The escalation/de-escalation rules from the table will be used for each dose level evaluated; the patient numbers and DLTs do not carry over from cohort to cohort. As an example, within a cohort:

- If none of the 3 patients experience a DLT → escalate the dose (“E” at column 3 row 0) to the next dose level cohort.
- If 1 out of 3 patients experience a DLT → de-escalate to a lower dose level (“D” at column 3 row 1).
- If 2 out of 3 patients experience a DLT → the dose is determined to be unacceptably toxic and will not be used again, de-escalate to a lower dose level (“DU” at column 3 row 2).
- If 1 out of 5 patients experience a DLT → stay at the same dose level (“S” at column 5 row 1).

The following rules apply during dose escalation:

- Starting dose at Cohort 1 is **100** mg.
- Although in the mTPI-2 method the cohort size is not fixed, at least 3 patients will be enrolled at each dose level. When all patients at a dose level complete DLT assessment, the study will escalate to the next dose level and another minimum of 3 patients will be recruited in this order until RP2D or MTD ([Table 5](#)).
- The sample size of a dose cohort that has already passed the preliminary DLT assessment (3 to 6 patients) and shown efficacy (eg, to include other efficacy signal for each tumor type) can be extended to 12 patients in order to further evaluate the safety and efficacy signals of that particular dose.

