For the time-to-event endpoints, such as PFS, OS, and DoR, the median, 25%, and 75% percentile of time-to-event will be estimated using Kaplan-Meier method with their corresponding 95% CI. Additionally, for PFS and OS, estimates will be provided for the survival probability along with their 95% CIs, which are calculated using linear transformation (Brookmeyer 1982) at selected landmarks, for example, at 3, 6, 9, 12, and 18 months. The Kaplan-Meier plots will be produced for PFS and OS. The duration of follow-up will be calculated descriptively using the Kaplan-Meier method. In order to assess duration of follow-up for PFS and OS, Kaplan-Meier estimates will be calculated in the same way as in their analysis, while using a different censoring rule which reverses censoring indicator instead (ie, patients who have an event will be censored at the date of event). Patients who are censored will be assigned as an “event.”

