5. ANALYSIS METHODS

5.1. General Principles

5.1.1. General Methodology

In general, all efficacy, safety and PK variables will be summarized using descriptive statistics and graphs as appropriate. Continuous variables will be summarized by descriptive statistics (observed number (n), mean, standard deviation, minimum, 25% percentile (Q1), median, 75% percentile (Q3), and maximum). Categorical variables will be summarized in frequency tables (frequencies and percentages).

Time to event variable will be analyzed using Kaplan-Meier method and summarized with median, 25% and 75% percentiles with their corresponding 95% confidence intervals (CI) which are calculated from a log-log transformation based on the method by [Brookmeyer and Crowley \(1982\)](#). Individual data will be presented in patient listings.

Analyses will be implemented using SAS Enterprise® Version 8.3 or higher (SAS Institute, Cary, North Carolina, USA). The International Conference on Harmonization (ICH) numbering convention, i.e. ICH-E3, will be used for all tables and listings.

Unless otherwise specified, analyses will be summarized:

- Efficacy analysis: by dose level for escalation stage (part 1) and by disease type for dose expansion (part 2).
- Analysis besides efficacy: by dose level and total for escalation stage (part 1) and by disease type and total for dose expansion (part 2).

In addition, main efficacy analysis will be repeated by IDH naïve/treated status (as defined in [Section 5.2.4](#)) and dose level for escalation stage (part 1) and by disease type for dose expansion (part 2).

Analysis will be conducted on the basis of first dose of study drug that a patient received. Hence, all summary tables, listings, and figures (TLFs) will be presented by treatment groups as defined in [Table 13](#).

Table 13 Group Display in TLFs

Part of the study	Treatment Group	Treatment Description in Data Display
Part 1 - Dose Escalation	1	Cohort 1- XX mg
	2	Cohort 2- XX mg
	3	Cohort 3- XX mg
	4	Cohort 4- XX mg
	5	Cohort 5- XX mg
	6	Cohort 6- XX mg
	7	Cohort 7- XX mg
	8	Cohort 8- XX mg
Part 2 - Dose Expansion at HMPL-306 XX mg*	1	Cohort A: AML

*As only one patient at HMPL-306 [REDACTED] mg was enrolled in Part 2 Dose expansion Cohort A, this patient will be combined into Part 1 Dose escalation Cohort 8 [REDACTED] mg in all the summary tables and figures.

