5.2.9. Efficacy Analyses

All efficacy analyses will be based on the efficacy analysis set. The response evaluable analysis set will be used to conduct sensitivity analysis for tumor response.

No formal comparison or hypothesis testing is planned for this study. Two-sided 95% confidence intervals (CIs) will be calculated in the applicable summary, unless otherwise specified.

Main efficacy analysis will be repeated by IDH naïve and treated status based on efficacy analysis set.

All efficacy data will be listed.

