5.2.9.2. DoCR/DoOR, EFS, PFS, and OS

For the time to event endpoints, such as various DoCRs/DoOR defined in [Section 4.2.3](#), EFS and EFS for patients with CR by 24 weeks (if data allowed) defined in [Section 4.2.5](#), OS defined in [Section 4.2.6](#), and PFS defined in [Section 4.2.7](#), the 25%, 50% (median), and 75% percentile of time-to-event will be estimated using Kaplan-Meier method with their corresponding 95% CI which are calculated from a log-log transformation based on the method by [Brookmeyer and Crowley \(1982\)](#). For PFS and OS, additionally, estimates will be provided for the survival probability along with their 95% CIs which are calculated using linear transformation based on the

method by [Brookmeyer and Crowley \(1982\)](#) at selected landmarks, for example, at 3, 6, 9, 12, and 18 months. The Kaplan-Meier plots will be produced for PFS and OS.

The duration of follow-up for PFS will be summarized by reversed Kaplan-Meier method (i.e. using different censoring rule which reverses censoring indicator of PFS, i.e. patients who progressed or died in PFS analysis will be censored at the date of progression or death, patients who are censored in PFS analysis will be assigned indicator of “event” with the same duration for PFS.) to calculate median, first and third quartiles and 95% CIs. The duration of follow-up for DoCR/DoOR, EFS, OS will be summarized similarly.

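### Landmark PFS and OS intervals use the linear form, which covers well below 95% and can leave 0–100% at these cohort sizes

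*SAP*

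**What the plan says.** SAP 5.2.9.2 uses two scales on the same Kaplan-Meier curves. The quartiles of every time-to-event endpoint get a "95% CI which are calculated from a log-log transformation based on the method by" the cited reference, and SAP 5.1.1 repeats this. The next sentence gives, for PFS and OS, the "survival probability along with their 95% CIs which are calculated using linear transformation based on the" same reference, "at selected landmarks, for example, at 3, 6, 9, 12, and 18 months". Protocol 9.2.7 also prescribes the "survival probability along with their 95% CIs, which are calculated using linear transformation" for the landmarks, so the SAP follows the protocol here. In both reference lists the title of the cited paper concerns the median survival time, not survival at a fixed time. Neither document says why the landmarks get the linear form, how limits outside 0–100% are handled, or what is shown when the estimate is 0% or 100%.

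Under SAP 5.1.1, Part 1 efficacy is shown for each dose level with no total column, and it is repeated by prior IDH-inhibitor status. Protocol 4.1.1 states that "at least 3 patients will be enrolled at each dose level" and lets a cohort be extended to 12. SAP 5.1.1 also records that Part 2 enrolled one patient, who is merged into Cohort 8.

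**The concern.** The linear interval is the estimate plus or minus 1.96 Greenwood standard errors. It treats the Kaplan-Meier estimate as roughly normal on the probability scale, which is a poor approximation with 3 to 12 patients. Two failures follow: true coverage falls below the stated 95%, and limits can drop below 0% or rise above 100%.

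Protocol 9.1.1 plans no hypothesis test and makes the 95% interval the measure of precision for efficacy. If its coverage is nearer 80%, the report overstates how well survival at each dose is known. Both documents allow accrued data to inform the design of a later study, where these figures could be reused.

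**Working it through.** **Inputs.**
- Two-sided 95% intervals, z = 1.96 (SAP 5.2.9).
- Linear landmark form (SAP 5.2.9.2, protocol 9.2.7).
- Group sizes 3 to 12 (protocol 4.1.1). Actual cohort sizes are not in the documents.
- One-year survival of 8% in refractory AML (protocol 2.3.1), the only background landmark survival figure relevant to AML. Other true values are assumptions, taken over a range up to 90%.

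**The plan's own figures.** The documents give no precision or coverage figure for the landmarks. Their binomial probabilities for n = 10 reproduce. At least one AE: 65.1%, 40.1% and 9.56%. CR at a true 20%: at least one 89.3%, at least two 62.4%, none 10.7%.

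**Formulas.** With no censoring before the landmark, the Kaplan-Meier estimate is S = x/n and Greenwood's variance is S(1−S)/n.
- Linear: S ± 1.96·√(S(1−S)/n).
- Log-log: S^exp(±1.96·√((1−S)/(nS))/|ln S|).
- Exact (Clopper-Pearson) at x = 0: 0 to 1 − 0.025^(1/n). At x = n: 0.025^(1/n) to 1.

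**Limits.**

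| Survivors | Linear (%) | Log-log (%) |
|---|---|---|
| 1/3 | -20.0 to 86.7 | 0.9 to 77.4 |
| 2/3 | 13.3 to 120.0 | 5.4 to 94.5 |
| 2/6 | -4.4 to 71.1 | 4.6 to 67.6 |
| 5/6 | 53.5 to 113.2 | 27.3 to 97.5 |
| 2/10 | -4.8 to 44.8 | 3.1 to 47.5 |
| 5/10 | 19.0 to 81.0 | 18.4 to 75.3 |
| 9/10 | 71.4 to 108.6 | 47.3 to 98.5 |

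At n = 3 every estimate strictly between 0 and 1 gives a limit outside 0–100%. At n = 6 four of the five do. At n = 10 and 12 it happens for 1, 2, n−2 or n−1 survivors. At n = 10 the chance of an out-of-range limit is 57% at a true survival of 20% or 80%, 36% at 30% or 70%, and 11% at 50%.

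**Coverage, one case by hand (n = 6, true S = 0.5).** The probabilities of x = 0 to 6 are 1, 6, 15, 20, 15, 6 and 1 over 64. The linear interval misses at x = 1 (upper limit 46.5%) and x = 5 (lower limit 53.5%). It has zero width at x = 0 and 6. Coverage is (64 − 6 − 6 − 1 − 1)/64 = 50/64 = 78.1%. Log-log fails only at x = 0 and 6, giving 62/64 = 96.9%.

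**Coverage more widely (%).** Estimates of 0% or 100% count as misses unless the exact limit is supplied.

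| n | True S | Linear | Log-log | Linear + exact at 0/1 | Log-log + exact at 0/1 |
|---|---|---|---|---|---|
| 3 | 0.5 | 75.0 | 75.0 | 100.0 | 100.0 |
| 3 | 0.8 | 48.0 | 38.4 | 99.2 | 89.6 |
| 6 | 0.08 | 38.5 | 38.5 | 99.1 | 99.1 |
| 6 | 0.5 | 78.1 | 96.9 | 78.1 | 96.9 |
| 6 | 0.7 | 87.1 | 81.2 | 98.9 | 93.0 |
| 10 | 0.08 | 56.0 | 56.0 | 99.4 | 99.4 |
| 10 | 0.3 | 84.0 | 96.1 | 86.8 | 98.9 |
| 10 | 0.5 | 89.1 | 94.4 | 89.1 | 94.4 |
| 10 | 0.7 | 84.0 | 92.4 | 86.8 | 95.3 |
| 10 | 0.8 | 88.6 | 86.0 | 99.4 | 96.7 |
| 12 | 0.3 | 87.6 | 97.7 | 87.6 | 97.7 |
| 12 | 0.5 | 85.4 | 97.8 | 85.4 | 97.8 |

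I ran n = 3, 4, 6, 8, 10 and 12 against S = 0.08, 0.2, 0.3, 0.5, 0.7, 0.8 and 0.9, which is 42 cells. The planned linear interval is below 95% in all 42. Log-log with the exact limit at 0% and 100% is higher than the planned interval in all 42.

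**With censoring.** This check used 20,000 simulated samples per setting, with exponential survival and censoring uniform between 0.5 and 2 times the landmark (an assumption). At a true 50%, linear against log-log is 78.0% v 93.6% (n = 6), 88.5% v 95.4% (n = 10) and 88.3% v 95.9% (n = 12).

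**The case against.** The strongest objection is that log-log by itself is not a general improvement. Its gain is in mid-range survival with about 6 or more patients. Part 1 plans 24 to 30 evaluable patients over 8 dose levels, so the average cohort is 3 to 4. In the 14 cells at n = 3 and 4, log-log alone ties with linear in 9, is higher in 3 and lower in 2. It also loses at n = 10, S = 0.8 (86.0% v 88.6%), and gains nothing at the documents' 8% one-year survival. There the loss comes from estimates of exactly 0%, where both forms fail. All of this stands, and it is why the log-log switch should not be made without the rule for 0% and 100%.

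The converse also fails. Keeping linear and adding only the exact limit leaves 78.1% at n = 6, S = 0.5 and 85.4% at n = 12, S = 0.5, and it does nothing about impossible limits. In some cells that combination covers more than the proposed one (n = 6, S = 0.7: 98.9% v 93.0%), but it does not hold up in the middle range.

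Three further points are fair. A quartile of time and a probability at a fixed time are different quantities, so using two scales is not a contradiction in itself; the case rests on performance. Not every interval is affected by the range problem, since mid-range estimates at n = 10 and 12 stay inside 0–100%. And the study is descriptive: there is no test, no decision rule on landmark survival, and the efficacy data are listed in full. That limits the consequences but does not make a nominal 95% label correct.

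**Conclusion.** The concern holds. For groups of 3 to 12 the planned interval covers less than its stated 95% in every case examined: 48–75% at n = 3, 72–87% at n = 6, 84–89% at n = 10 and 85–91% at n = 12, for true survival between 20% and 80%. It gives impossible limits for many small-cohort results. By n = 30, without censoring, it is near nominal over the same range (94.6–95.7%), so this is a small-sample problem, and the plan reports small samples.

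The result rests on the 3-to-12 range in protocol 4.1.1 and on exact enumeration without censoring; the censored simulation agrees at a true 50%. No formal decision changes, so it should be corrected but does not threaten the study's conclusions.

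**What to change.** In SAP 5.2.9.2, compute the landmark PFS and OS intervals on the log-log scale, and add one sentence: where the estimate is 0% or 100% with no earlier censoring, report the Clopper-Pearson limits. For 0 of n these are 0% to 70.8% at n = 3, 45.9% at n = 6 and 30.8% at n = 10. Where such an estimate follows earlier censoring, mark the interval not estimable and print the number at risk. SAP 5.2.9.1 and 5.2.9.4 already use Clopper-Pearson for response rates and transfusion endpoints.

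List the departure from protocol 9.2.7 in SAP section 7; align the protocol wording if it is amended for other reasons. Replace the reference cited for the landmark interval with one that covers survival at a fixed time. Truncating limits to 0–100% is not a substitute, because it hides the range problem and leaves coverage unchanged.

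The cost is one software option, a short rule for 0% and 100%, and one line in section 7. No new data are needed.

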5.2.9.3. Time to response

For the various TTCRs/TTOR defined in [Section 4.2.4](#), descriptive statistics will be provided.

5.2.9.4. Baseline Transfusion Dependence and Post-baseline Transfusion Independence

For the baseline TD and post-baseline TI defined in [Section 4.2.8](#), the number and percentage of patients in each endpoint will be summarized descriptively. Clopper-Pearson exact method will be used to construct the two-sided 95% exact CIs.

In addition, shift tables between the baseline TD and post-baseline TI will be provided.

5.2.10. Exposure of Study Treatment

Exposure of study treatment described in [Section 4.3](#) (duration of exposure, actual duration of exposure, cumulative dose, dose intensity, relative dose intensity, relative dose intensity category, and percentage intended dose for study drug) will be summarized on safety analysis set.

The following summary for dose modification will also be summarized.

- Number of patients with any dose modification (including both drug interruption and dose reduction)
- Number of patients with any drug interrupted (number of patients experienced drug interruption and reasons for drug interruption)
- Number of patients with any dose reduced (number of patients with any dose reduction and reasons for dose reduction)

5.2.11. Safety Analyses

Unless otherwise specified, the safety data based on safety analysis set during the treatment period will be summarized, and the treatment period is defined as the duration from the date of the first study drug administration until 30+7 days (7-day window only applies to parameters collected by visit) or prior to the start of a subsequent anti-tumor therapy (whichever comes first) after last dose.

5.2.11.1. Dose-Limiting Toxicity (DLT)

DLT analysis will be performed for the Part 1 based on the DLT evaluable analysis set.

In addition to summarizing number and percentage of patients with DLTs, DLTs will also be summarized by SOC, PT, and highest CTCAE grade based on the DLT evaluable analysis set.

DLTs will be listed.

5.2.11.2. Adverse Events

TEAE overview

An overall summary of TEAEs will include the number of patients with:

- Any TEAE
- Any TEAEs by maximum CTCAE grade
- Any TEAE of CTCAE Grade 3 or higher
- Any TEAE Leading to Dose Modification
- Any TEAE Leading to Dose Reduction
- Any TEAE Leading to Drug Interruption
- Any TEAE Leading to Drug Discontinuation
- Any TEAE Leading to Death
- Any Treatment Related TEAE
- Any Treatment Related TEAE of CTCAE Grade 3 or higher
- Any Treatment Related TEAE Leading to Dose Modification
- Any Treatment Related TEAE Leading to Dose Reduction
- Any Treatment Related TEAE Leading to Drug Interruption
- Any Treatment Related TEAE Leading to Drug Discontinuation
- Any Treatment Related TEAE Leading to Death
- Any Serious TEAE
- Any Treatment Related Serious TEAE
- Any Special Interest TEAE (AESI)
- Any Treatment Related AESI

TEAE Summary

The following categories will be summarized (the number and percent of patients) by SOC, PT and maximum CTCAE grade (All Grade, Grade ≥ 3 , Grade 1/2, Missing Grade).

	Summary scope
TEAE	
- Any TEAE- TEAEs with CTCAE grade 3 or higher (maximum CTCAE grade by Grade 5, Grade 4, Grade 3, Missing Grade)- TEAEs leading to dose modification
o TEAEs leading to dose interruptiono TEAEs leading to dose reduction- TEAEs leading to discontinuation of study drug- TEAEs leading to death (by SOC and PT only)
Treatment-related TEAE	
- Any treatment-related TEAE- Treatment-related TEAEs with CTCAE grade 3 or higher (maximum CTCAE grade by Grade 5, Grade 4, Grade 3, Missing Grade)- Treatment-related TEAEs leading to dose modification
o Treatment-related TEAEs leading to dose interruptiono Treatment-related TEAEs leading to dose reduction

	Summary scope
	
– Treatment-related TEAEs leading to discontinuation of study drug– Treatment-related TEAEs leading to death (by SOC and PT only)
Serious TEAE	
– All serious TEAE– Treatment-related serious TEAEs

In addition, all TEAE and treatment-related TEAE will also be summarized (the number and percent of patients) by PT and maximum CTCAE grade (All Grade, Grade ≥ 3 , Grade 1/2, Missing Grade).

All TEAE and TEAE with CTCAE grade 3 or higher will also be summarized by SOC and PT.

If a subject experienced the same adverse event (as identified by MedDRA preferred term) more than once during the study, the worst occurrence (e.g. worst grade) will be counted. Similarly, if a subject experienced more than one occurrence of the same SOC/PT, the worst occurrence (e.g. worst grade) will be counted within a particular SOC/PT. When summarizing AE by CTCAE grade, if a subject experienced more than one occurrence of the same SOC/PT, the worst severity grade will be counted. Each summary will be ordered by descending order of incidence of SOC and PT within each SOC. If the frequencies of SOC/PT tie, an alphabetic order of SOC/PT will be applied.

AESI Summary

AEs of special interest (AESI) are listed in the below table, and will be identified by MedDRA Query (SMQ)/PT:

AESI	Search Strategy
Abnormal hepatic function	Drug related hepatic disorders - comprehensive search (SMQ Code 20000006 Narrow search)
Differentiation syndrome	Differentiation syndrome (PT Code 10080638)

Abbreviations: AESI = adverse event of special interest; PT = preferred term; SMQ = standard MedDRA query.

All AESIs will be summarized in frequency and percentage by AESI category, PT and maximum CTCAE grade (All Grade, Grade ≥ 3 , Grade 1/2, Missing Grade). The following overall safety summary will also be summarized for each AESI category:

- AESI
- Treatment Related AESI
- AESI of CTCAE Grade 3 or higher
- AESI meeting SAE criteria
- AESI leading to dose modification
- AESI leading to dose reduction

- AESI leading to dose interruption
- AESI leading to dose discontinuation
- AESI leading to death

Moreover, time to AESI onset (days), AESI duration (days) and AESI outcome (the number and percent of patients) will be summarized descriptively.

Time to AESI onset is defined as the time interval from the date of first dose of study drug to the earliest onset date among all AESIs. That is, if a subject has multiple AESI occurrences, the earliest AESI onset date will be used as the onset date to calculate time to onset of AESI.

AESI duration (days) will only be calculated for ended AESI as (AE end date-AE start date+1).

Concomitant medication taken for hepatic function abnormal will be summarized by ATC and PT, and listed.

COVID-19 AE

COVID-19 AE will be identified by the following MedDRA Query (SMQ), and will be summarized (the number and percent of patients) by PT and maximum CTCAE grade (All Grade, Grade ≥ 3 , Grade 1/2, Missing Grade).

COVID-19	Search Strategy
COVID-19	COVID-19 (SMQ Code 20000237 Narrow search)

AE Listing

All AE will be listed. All AE information including AE term, start date, end date, severity, whether the AE is DLT, CTCAE grade, whether the AE is SAE, classification of SAE (if SAE), whether the AE is AESI, relationship to study drug, action taken, outcome, whether this event is considered as part of Differentiation Syndrome will be presented in subject data listings. If the AE is ongoing at the data cut-off date, it will be reported as 'Ongoing' in the listing.

In addition, separate listings of (1) all TEAEs of CTCAE Grade 3 or higher, (2) all treatment related AEs, (3) all SAEs, (4) all AEs leading to discontinuation of study drug, (5) all AEs leading to dose modification, (6) all AEs leading to death, (7) all AESIs, (8) COVID-19 AEs will be provided.

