9.2.4 Safety Analysis

The summary of the exposure to study treatment, AEs, AESIs, AEs leading to drug modification or discontinuation including DLTs, changes in laboratory results, and changes in vital signs, etc, will be presented. The severity of all AEs will be graded according to NCI CTCAE v5.0, and the AE verbatim term will be coded by the Medical Dictionary for Regulatory Activities (MedDRA).

TEAEs are defined as AEs that started or worsened in severity on or after the first dose of study treatment and no later than 30 days after the end of treatment.

Only those AEs that were treatment-emergent will be included in summary tables. All AEs, treatment-emergent or otherwise, will be presented in patient data listings. The number and frequency of patients experiencing adverse events will be summarized according to system organ class (SOC) and preferred terms. If a patient reports a TEAE more than once within that SOC/preferred term, the AE with the highest severity will be used in the corresponding severity summaries.

The following safety summaries will be produced:

- Overview of AEs
- Summary of DLTs (dose escalation part)
- Summary of TEAEs
- Summary of serious TEAEs
- Summary of AESIs
- Summary of TEAEs leading to dose interruption, dose reduction, or termination of treatment

The above summaries will be repeated for TEAEs related to study treatment.

Drug exposure including number of cycles received, total duration of exposure, cumulative dose received (mg), dose intensity, and relative dose intensity will be summarized. The number and percentage of patients requiring dose interruption, dose delay, dose reduction, and treatment discontinuation because of AEs will be summarized. Reasons for dose modifications will also be summarized.

For laboratory tests that are graded by NCI CTCAE v5.0 or higher, results will be summarized by grade. Treatment-emergent changes will be summarized by maximum post-baseline grade. A shift table summarizing the shift from baseline to maximum post-baseline grade will be presented.

The changes in vital signs and ECOG PS scores from baseline will be summarized. Changes in 12-lead ECG (for example, changes in QTcF) will be summarized.

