5.2.11.4. Laboratory Evaluations

For hematology, chemistry and coagulation labs, the observed values and change from baseline will be summarized by scheduled visit using descriptive statistics. For selected qualitative laboratory test (if any), number and percentage of patients with categorical results will be summarized for each scheduled visit.

Toxicities for clinical labs will be characterized according to NCI CTCAE, v5.0, and shift in grade from baseline to the worst post-baseline value will be summarized. Both the scheduled and unscheduled assessments will be used to identify the worst post-baseline values.

Shift table from baseline to worst post-baseline value according to abnormality (Normal / Abnormal, Not Clinically Significant / Abnormal, Clinically Significant) assessed by investigator will be provided.

The number and percentage of patients satisfying abnormal hepatic laboratory values categories defined in [Section 4.4.3](#) will be summarized.

Listings of all laboratory data with normal reference ranges, and CTCAE grades (when possible) will be provided.

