5.2.11.9. Differentiation Syndrome

Besides DS analysis as an AESI category described in [Section 5.2.11.1](#), the following analysis will also be provided.

The number and percent of patients experiencing differentiation syndrome (DS) will be summarized. The number and percent of patients with following DS symptoms will be summarized:

- Dyspnea
- Unexplained fever
- Weight gain
- Unexplained Hypotension
- Acute renal failure
- Interstitial lung infiltration or pericardial effusion

In addition, the number and percent of patients with the Montesinos grading will also be summarized, the grading includes two grade level as moderate (2-3 symptoms) and severe (4 or more symptoms).

DS will be summarized by symptoms, Montesinos grade, and CTCAE grade.

Concomitant medication taken for DS will be summarized by ATC and PT, and listed.

A by-patients listing of differentiation syndrome will be listed.

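### Read literally, the SAP's time to AESI onset takes one date per patient across abnormal hepatic function and differentiation syndrome, and should be defined within each category

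*SAP*

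**What the plan says.** SAP Section 5.2.11.2 (AESI Summary) identifies AESIs by a search table with two entries: abnormal hepatic function, found by a narrow hepatic SMQ, and DS, found by a single preferred term. Frequencies are planned by AESI category. An overview of nine count rows follows, introduced by "The following overall safety summary will also be summarized for each AESI category".

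A new sentence then adds three more items: "Moreover, time to AESI onset (days), AESI duration (days) and AESI outcome (the number and percent of patients) will be summarized descriptively". It does not mention category. Onset is defined as the interval "from the date of first dose of study drug to the earliest onset date among all AESIs", and the SAP explains that a patient with several AESI occurrences contributes the earliest date. Duration is defined separately, event by event, for AESIs that have ended.

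Section 5.2.11.9 adds further DS analyses. It opens with "Besides DS analysis as an AESI category described in" and then names Section 5.2.11.1, which covers dose-limiting toxicity. Protocol Section 9.2.4 asks for a "Summary of AESIs" and says nothing about onset.

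**The concern.** Abnormal hepatic function and DS are different harms with different management. Protocol Section 7.6.1 gives DS its own handling rules, including immediate dexamethasone and criteria for interrupting study drug, so when DS tends to appear is useful to know. Protocol Section 8.1.4 has sites record the time of DS diagnosis, so the data to describe DS onset will exist. That is a data-capture rule, not a promise of an analysis.

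A time to the first AESI of either kind describes neither harm. If a hepatic event comes first, it hides the DS onset, and the reverse. Patients with only one harm also go into a single mixed distribution that does not show which harm each time belongs to. Safety is the primary objective of both parts of the study, so the safety tables should be readable harm by harm.

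**Working it through.** The plan gives no figure to reproduce and no AESI rates, so this is a check of the text, with simple algebra to show what the literal rule does.

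**Step 1. What each place plans.**

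| Place | Content | By category? | Onset summary? |
|---|---|---|---|
| SAP 5.2.11.2, frequencies | Counts and percentages by term and maximum grade | Yes | No |
| SAP 5.2.11.2, overview | 9 rows: any AESI; treatment related; Grade 3 or higher; serious; leading to dose modification, reduction, interruption, discontinuation, death | Yes | No |
| SAP 5.2.11.2, onset | Earliest AESI date per patient | Not stated; defined over all AESIs | Yes |
| SAP 5.2.11.2, duration | End date minus start date plus 1, per ended event | Not stated | No |
| SAP 5.2.11.2, outcome | Number and percentage | Not stated | No |
| SAP 5.2.11.9 | DS counts, symptoms, grades, concomitant medication, listing | DS only | No |
| SAP 4.4.3 and 5.2.11.4 | Patients crossing hepatic laboratory thresholds | Hepatic laboratory values only | No |
| SAP 5.2.11.2, listings | Start and end date of each event | Per event | Listing only |
| Protocol 9.2.4 | General AESI summary | Not stated | No |

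The two places where a harm-specific onset summary might have been found plan other things. For DS: "DS will be summarized by symptoms, Montesinos grade, and CTCAE grade". For the liver: "The number and percentage of patients satisfying abnormal hepatic laboratory values categories defined in" Section 4.4.3. The only planned onset summary is therefore the one whose wording is in question.

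**Step 2. What the literal rule does to one patient.** Let H be the time from first dose to the first hepatic AESI and D the time to the first DS event. The literal rule reports

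T = min(H, D).

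A patient with H only contributes H, and a patient with D only contributes D. A patient with both contributes only the smaller. With assumed values H = 10 days and D = 40 days, T = min(10, 40) = 10, and the 40 enters no summary. Defined within category, the same patient contributes 10 to the hepatic row and 40 to the DS row: two onset dates in place of one.

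**Step 3. What it does to the table.** Let a be the number of patients with any hepatic AESI, b the number with DS, and c the number with both. The literal rule uses a + b − c dates, whereas the by-category rule uses a + b. The difference is

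(a + b) − (a + b − c) = c.

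The documents give no value for a, b or c, so c cannot be estimated and no count is claimed.

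**Step 4. Which of the three added items carry the pooling wording.** Only onset does. Duration is computed per event and merges nothing. Outcome is simply silent on category.

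**The case against.** The strongest reply is that the pooled reading is the less natural one. The AESI Summary is organised by category, and the sentence on onset continues from rows that are explicitly by category. The explanatory sentence about several occurrences reads like an ordinary first-occurrence rule for repeated events, which would be needed within the hepatic category alone because an SMQ can return several terms and episodes per patient. Section 5.2.11.9 also refers to DS as an AESI category. All of this makes a within-category intent plausible. It does not settle the matter, because the definition itself runs over all AESIs and nothing limits it to a category. A programmer following the definition would pool, and one inferring the intent would split. A reader might infer that the sponsor has decided to merge the two harms, but the documents do not support that.

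The reply is also right that little information is lost. Section 4.1.1 derives study day from first dose for showing when events start and stop, the AE and AESI listings carry start dates, and DS has its own listing. Part 1 expects about 24 to 30 evaluable patients over up to eight dose levels, so onset can be read from the listings by hand.

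Three further inferences should be avoided:

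- **Duration and outcome are defined wrongly.** They are not. A by-category layout for them is a matter of consistent presentation.
- **A protocol commitment is missed.** Protocol 9.2.4 specifies no onset analysis; the SAP added this item itself.
- **The wrong cross-reference is evidence of pooling.** Section 5.2.11.1 concerns another subject ("DLT analysis will be performed for the Part 1 based on the DLT evaluable analysis set"), so the reference is a clerical slip, evidently for 5.2.11.2.

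**Conclusion.** The point holds as a low-impact defect of wording. As written, the SAP's only onset summary for AESIs pools two unrelated harms into one date per patient, and neither document plans an onset summary specific to either harm. The effect is confined to one descriptive summary. No test, dose decision or DLT evaluation depends on it, and the event dates stay in the listings.

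This rests on reading the definition literally, and on the two documents alone; the table shells are not among them. If the shells already show onset by category, the change only brings the text into line with them. The number of patients whose later onset would be hidden is unknown. It is zero if no patient has both harms, but even then the pooled summary would not show onset for each harm.

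**What to change.** In SAP Section 5.2.11.2, define time to AESI onset as the interval from first dose to *the earliest onset date among all AESIs within each AESI category*, and add the same restriction to the explanatory sentence on multiple occurrences. Present onset separately for DS and abnormal hepatic function, with duration and outcome in the same by-category layout. If a combined row is wanted, label it *any AESI*.

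Separately, as a clerical correction, change the cross-reference in Section 5.2.11.9 from 5.2.11.1 to 5.2.11.2.

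The cost is a few words of SAP text, by-category rows in one table and one corrected section number. No new data are needed.
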